12.4.4. Analysis of Secondary Outcomes

The statistical and analytical methods that will be used to evaluate the secondary endpoints are described in this section.

12.4.4.1. Secondary Outcome: Hospitalization or Death Within 28 Days

The proportion of those progressing to hospitalization or death within 28 days of randomization will be compared between treatment groups using logistic regression (Ge 2011). All participants in the ITT population will be included in this analysis. Covariates in the analysis will include age. Site will be included as a random effect. The risk difference and 95% confidence interval will be estimated. Supportive analysis of this outcome will use the antiviral efficacy analysis population and the PP population.

12.4.4.2. Clinical Status (Disease Progression)

The distribution of ordinal scale severity results will be summarized by treatment arm as percentages in the ITT population. A proportional odds model will be used to compare groups on this ordinal scale. The common odds ratio measures the effect size and is valid under the proportional odds assumption that will be verified via a goodness of fit likelihood ratio test. The model will include fixed effects for treatment, and age. Hypothesis tests for the model are nearly identical to the Wilcoxon Rank Sum test. Supportive analysis of this outcome will use the antiviral efficacy analysis population and the PP population.

12.4.4.3. Secondary Outcome: Oxygen Saturation (O2 sat)

A logistic regression using generalized estimating equations will be used compare the proportion of subjects at or above 95% oxygen saturation (O2 sat) between LAM-002A versus placebo as measured on Days 1, 4 and 11 in participants in the ITT population. Individuals requiring respiratory assistance, hospitalized or who died will be considered as having O2 sat <93%. Those who require baseline O2 will be excluded from the analysis. Supportive analysis of this outcome will use the antiviral efficacy analysis population and the PP population.

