supplemental oxygen use, temperature, systolic blood pressure, heart rate, and AVPU (alert, voice, pain, unresponsive). Assessments will be performed on Day 1 (predose), Day 4, Day 11 and Day 28 during site visits.					
j. AEs will be described using concise medical terminology, including whether the AE is serious, the date of AE onset, the date of AE resolution, the severity of the AE based on the					
CTCAE, Version 5.0, a description of relatedness of the AE to study drug or to a study procedure, the action taken due to the AE, and the outcome of the AE. AEs will be collected					
beginning once ICF is executed and include any changes from medical history. Day 6, Day 8, and Day 22 assessments will be done via telephone					
k. Concomitant medication assessments should include information regarding all prescription, nonprescription, and alternative medications (health foods). Use of any other drugs					
intended as therapy for COVID-19 (e.g. antivirals, antimalarials, BTK inhibitors, anti-IL-6 antibodies) or supportive care (e.g. antidiarrheals, NSAIDs, antiemetics, supplemental					
oxygen) should be noted. Information on concomitant medications used during Screening or since the last assessment will be assessed on each designated day. Day 6, 8, and 22					
assessments will be done via telephone					
1. 12-lead ECG will be obtained with the subject resting in a supine position at Screening. An ECG obtained within 30 days prior to the Screening visit is acceptable.					
m. At Screening, obtain a subject number. On Day 1, randomize the subject and obtain a study drug bottle number.					
n. I ne first dose of blinded study drug (LAM-002A or placebo) will be administered to the subject in the study center (with recording of the date and actual clock time of the LAM 002A administration). Depending on the time of administration (AM vs PM), the follow we visit times will be determined as AM = PM.					
LAW-002A administration]. Depending on the time of administration (AW vs PW), the follow-up visit times will be determined as AW of PM.					
o. Study personner win dispense the remainder of the 10-day supply of binded study drug (LAM-002A or placedo) to the subject with instructions for self-administration at nome.					

Table 1:Schedule of Activities

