4.2.4. Oxygen Saturation

• Proportion of subjects at or above 95% oxygen saturation (O2 sat) between LAM-002A versus placebo as measured on Days 1, 4, and 11.

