6.2. Exclusion Criteria

Study candidates who meet any of the following criteria will not be eligible for participation in this study:

- 1. Respiratory rate ≥ 20 breaths per minute.
- 2. Oxygen saturation by pulse oximetry $\leq 93\%$ on room air or requirement for supplemental oxygen to maintain oxygen saturation >93%.
- 3. Total NEWS score ≥ 6 or presence of a score of 3 on any of the individual NEWS parameters.
- 4. Radiographic evidence of pulmonary infiltrates (clinical X-ray within 2 days of referral)
- 5. Hepatic profile showing any of the following:
 - Serum alanine aminotransferase (ALT) >5 × upper limit of normal (ULN) (CTCAE Grade ≥3).
 - Serum aspartate aminotransferase (AST) $>5 \times$ ULN (CTCAE Grade \geq 3).
 - Serum bilirubin >1.5 × ULN (CTCAE Grade \geq 2).
- 6. Renal profile showing an estimated creatinine clearance (eClCR) <30 mL/minute (with eClCR to be calculated by the method at the laboratory performing the serum creatinine test).
- 7. Presence of a cancer with disease manifestations or therapy that could adversely affect subject safety or longevity, create the potential for drug-drug interactions, or compromise the interpretation of study results.
- 8. Significant cardiovascular disease (e.g. myocardial infarction, arterial thromboembolism, cerebrovascular thromboembolism) within 1 month prior to start of study therapy; unstable angina; symptomatic peripheral vascular disease; CTCAE Grade ≥2 congestive heart failure; or uncontrolled CTCAE Grade ≥3 hypertension (diastolic blood pressure ≥100 mmHg or systolic blood pressure ≥160 mmHg) despite antihypertensive therapy.
- Significant screening ECG abnormalities, including atrial fibrillation/flutter, 2nd degree atrioventricular (AV) block type II, 3rd-degree AV block, Grade ≥2 bradycardia, or corrected QT (QTc by Fridericia [QTcF]) >480 msec (Grade >1).
- 10. Gastrointestinal disease (e.g. gastric or intestinal bypass surgery, pancreatic enzyme insufficiency, malabsorption syndrome, symptomatic inflammatory bowel disease, chronic diarrheal illness, bowel obstruction) that might interfere with drug absorption or with interpretation of gastrointestinal AEs.
- 11. Pregnancy or breastfeeding.
- 12. Prior solid organ transplantation.

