7. STUDY DRUG ALLOCATION

7.1. Randomization

After a subject has completed the necessary screening assessments and has been confirmed to be eligible, the subject can be randomized into the study. In order to obtain a treatment arm assignment for a subject, a site representative will submit the appropriate information for randomization, and the system will make an assignment of a study drug bottle number. Subjects will be randomized in a 1:1 ratio (Arm A:Arm B) to either of the following treatment assignments:

- Arm A: LAM-002A
- Arm B: Placebo

In order to balance treatment allocation, a permuted block centralized randomization will allocate subjects.

It is anticipated that subjects will usually begin study drug immediately after randomization Day 1 of the study. In case of administrative delays, every attempt should be made to initiate study drug treatment by Day 2.

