12.2. Sample Size Determination

The study is designed to have high power at a moderate significance level to detect a signal of benefit for the viral load outcome. The sample size calculation is based on the primary endpoint of interest: log₁₀ respiratory (nasopharyngeal swab) viral load at Day 4 post-randomization.

Given the limited data on the variability of the change in log_{10} viral load, the study is powered based on detecting a moderate standardized effect size of 0.3 using an analysis of covariance (ANCOVA), adjusting for baseline log_{10} viral load. (NOTE: For ANCOVA, the effect size is the standard deviation of the treatment means divided by the pooled standard deviations of the observations. An ANCOVA standardized effect size of 0.3 is equivalent to a Cohen's d of 0.60). To be conservative, a R-squared of 0 between the log_{10} viral RNA at 4-days and baseline log_{10} viral RNA was assumed. With a power of 90%, and a type I error rate of 20% (2-sided), it will be possible to detect the hypothesized 0.3 standardized effect size with 74 total patients – 37 patients per group with a 1:1 randomization. We will enroll a sample size of 142 to assure that a sufficient number of participants with baseline viral load >10⁵ copies/ml. The table below shows the power to detect an effect size of 0.3 given 10% loss to follow-up and various proportions enrolled with baseline viral load >10⁵ copies ml.

	Proportion of Enrolled Participants with >10⁵ copies/ml						
	0.40	0.50	0.60	0.70	0.80	0.90	1.00
Power to Detect Effect Size of 0.3	0.79	0.86	0.91	0.94	0.96	0.97	0.98

Based on available data regarding the distribution of viral load, it is conservatively estimated that \geq 50% of randomized participants will have a baseline viral load $>10^5$ copies/mL. The table above demonstrates that enrolling 142 will provide sufficient power even if the proportion with baseline viral load $>10^5$ copies/ml is as low as 40%. The prevalence of this subgroup will be monitored and adjustments to overall sample size may be made if necessary.

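### The oxygen-saturation analysis lists the pre-dose Day 1 reading as an outcome visit and names no post-baseline comparison

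*Combined protocol and SAP*

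**What the plan says.** The endpoint in section 4.2.4 is: "Proportion of subjects at or above 95% oxygen saturation (O2 sat) between LAM-002A versus placebo as measured on Days 1, 4, and 11". The synopsis and sections 3.2 and 3.2.4 name the same three days. Section 12.4.4.3 specifies a logistic regression with generalized estimating equations comparing the arms "as measured on Days 1, 4 and 11 in participants in the ITT population". It scores respiratory assistance, hospitalization and death as low saturation, and leaves out anyone on oxygen at baseline. It does not state visit terms, a treatment-by-visit term, the contrast to be tested, covariates or the working correlation.

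For vital signs, including pulse oximetry, Table 1 footnote i says: "Assessments will be performed on Day 1 (predose), Day 4, Day 11 and Day 28 during site visits". The Day 1 value therefore precedes treatment.

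Three other sections matter here:
- Section 12.4.2 says that no inferential statistics will be calculated for baseline characteristics.
- Section 12.4.3 also takes Day 1 as a response in the primary model, but it names a Day 4 contrast and says the difference is conditional on baseline.
- Section 12 defers full statistical detail to a SAP to be filed before database lock.

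**The concern.** Day 1 is one of three visits on which the arms are compared, yet randomized treatment cannot have affected it. The text allows two readings, and both cause trouble.

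- **One effect pooled over the three days.** A visit with a true effect of zero is averaged with two visits that can show an effect. The estimate is pulled toward no effect and power is lost.
- **A separate comparison on each day.** The Day 1 comparison then tests a chance pre-treatment difference and presents it under an efficacy endpoint, which sits badly with section 12.4.2.

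This is a named secondary efficacy endpoint. The risk is a real difference on Days 4 and 11 that is understated or missed, not a false positive.

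**Working it through.** **1. The plan's own figures.** No saturation rate, effect size, significance level or power is stated for this endpoint. The only sizing is for the primary endpoint in section 12.2: 2 × (1.2816 + 1.2816)² / 0.60² = 36.5, so 37 per group and 74 in total. That reproduces the plan, but it does not bear on this point.

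**2. Inputs.** From the documents: three visits of which one is pre-dose, 1:1 allocation, 142 enrolled and 10% loss to follow-up, giving 142 × 0.9 / 2 ≈ 64 per arm. Assumed because the documents give none: placebo rates, odds ratios, within-subject correlation and a two-sided level of 0.05.

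**3. Risk difference under one pooled effect.** With true differences (0, t, t) and equal visit weights, the pooled difference is (0 + t + t)/3 = 2t/3. One third is lost.

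**4. Log odds ratio under one pooled effect.** Worked example with a placebo rate of 0.70 on every day, an odds ratio of 2.5 on Days 4 and 11, and an independence working correlation:
- Odds on LAM-002A on Days 4 and 11: 2.333 × 2.5 = 5.833, a rate of 0.8537.
- Pooled rate on LAM-002A: (0.70 + 2 × 0.8537)/3 = 0.8024, odds 4.062.
- Pooled odds ratio: 4.062/2.333 = 1.741, with logarithm 0.554.
- Retained: 0.554/0.916 = 60%, a loss of 40%.

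Large-sample solutions of the estimating equations, for odds ratios from 1.2 to 3, give:

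| Placebo rates on Days 1, 4, 11 | Working correlation | Log odds ratio lost |
|---|---|---|
| Flat, 0.6 to 0.9 | Independence | 34-45% |
| Falling: 0.90, 0.85, 0.85 | Independence, or exchangeable up to 0.7 | 7-35% |
| Rising: 0.70, 0.75, 0.85 | Independence | 41-50% |

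With an exchangeable working correlation and flat rates the loss grows. At a placebo rate of 0.9 and odds ratio 2.5, the share retained is 53%, 47% and 33% at correlations of 0.3, 0.5 and 0.7.

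**5. Power, normal approximation.** The variance of a subject's mean over k equally correlated visits is proportional to (1 + (k − 1)ρ)/k. The test statistic from three visits, relative to Days 4 and 11 alone, is therefore (2/3) × √[3(1 + ρ) / (2(1 + 2ρ))]. Power of 80% at two-sided 0.05 corresponds to 1.960 + 0.842 = 2.802.

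| ρ | Ratio | 2.802 × ratio | Power |
|---|---|---|---|
| 0 | 0.816 | 2.288 | 63% |
| 0.5 | 0.707 | 1.981 | 51% |
| 1 | 0.667 | 1.868 | 46% |

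**6. Simulation check.** 64 per arm, independence working correlation, flat placebo rates, two-sided 0.05:

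| Placebo rate | Odds ratio | Latent correlation | Power, Days 4 and 11 | Power, pooled over three days |
|---|---|---|---|---|
| 0.7 | 2.5 | 0.3 | 0.80 | 0.55 |
| 0.8 | 3 | 0.6 | 0.70 | 0.41 |
| 0.7 | 2 | 0.9 | 0.45 | 0.23 |

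With no true effect, rejection rates were 0.048 to 0.056, so type I error holds. When Day 1 stayed in as a response but treatment-by-visit terms and a post-baseline contrast were used, estimates and power matched the Days 4 and 11 analysis.

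**The case against.** The strongest reply is that section 12.4.4.3 never states a pooled coefficient. It names a method and three days, the detail is deferred to the SAP, and the text can be read as a comparison on each day. Nor is Day 1 as a response an error in itself: the primary model does the same without dilution because it tests a Day 4 contrast. This stands, and it makes every dilution figure conditional. It does not remove the point, because the day-by-day reading tests a pre-dose difference, and because the objective, endpoint and analysis sections all list Day 1 as a visit for comparison.

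A reader might infer that the effect and its power are roughly halved. The documents do not support that as a general result. One null visit in three removes one third of the risk difference; a loss near one half or more needs particular assumed rates, odds ratios and correlations. The dilution may well be milder. Section 6.2 excludes saturation of 93% or below at entry, so few subjects may fail the 95% cut on Day 1, while hospitalization and death count as failures later. With assumed placebo rates of 0.90, 0.80 and 0.75, odds ratio 2.5 and an exchangeable GEE, about 70-75% of the log odds ratio was retained (300 runs).

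Comparing the pooled model with one that adjusts for Day 1 would also overstate the loss, because it includes the gain from covariate adjustment. Finally, section 12.4.1 has secondary results described by summary statistics, so no planned power is lost.

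**Conclusion.** The point holds in a conditional form. A pre-dose reading is listed as one of three outcome visits, and nothing in the section confines the treatment comparison to the post-dose days.

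Under a single pooled effect with equal visit weights, the one-third loss in the average risk difference is plain arithmetic. The losses in log odds ratio and the fall from 80% power to 46-63% rest on the assumptions shown above, not on figures in the plan. Under day-by-day comparison there is no dilution, but the Day 1 test is not evidence of efficacy. The error runs toward missing an effect.

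This is worth correcting on a named secondary endpoint. It does not touch the primary analysis.

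**What to change.** In section 12.4.4.3, define Day 1 saturation as baseline and base the treatment comparison on Days 4 and 11 only. Either of two models will do:
- Days 4 and 11 as outcomes, with Day 1 saturation as a covariate and day and treatment-by-day terms.
- Days 1, 4 and 11 as joint responses with treatment-by-visit terms and a stated contrast on Days 4 and 11, parallel to the primary model.

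State the chosen model, the contrast and the working correlation. Report Day 1 descriptively by arm. Make the same change of days in the synopsis and in sections 3.2, 3.2.4 and 4.2.4.

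The cost is wording only, since the Day 1 reading is already collected. There is one small downside. With a covariate, the odds ratio is conditional on baseline and is a different quantity from the marginal one. In a check with a flat 80% placebo rate and strong correlation, the log odds ratio moved from 0.96 to 1.24 (and power from 0.62 to 0.72). The difference in proportions on Days 4 and 11 should therefore be reported alongside it.

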12.4.5. Exploratory Endpoints

Analysis for exploratory endpoints will be defined in the study SAP or separate reports, as appropriate.

12.4.6. Subgroup Analyses

Heterogeneity of treatment effect (HTE) for the primary and secondary progression to hospitalization or death outcome will be examined for the following subgroup variables: days from onset of symptoms to randomization, NEWS score at randomization and sex (male vs. female). HTE will be evaluated within a mixed model for the primary outcome and a logistic regression for the secondary progression outcome. The models will include treatment, site, the subgroup variable, and the interaction of the subgroup variable with time. Differences in means or risk with 95% confidence intervals will be estimated for the treatment difference within each level of the subgroup variable. The significance test of the interaction will be used to formally test HTE at the two-sided 0.05 significance level.

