The primary analysis will test whether the viral load in nasopharyngeal samples is lower at Day 4 in those receiving LAM-002A compared to placebo. All participants in the antiviral efficacy analysis set (i.e. the subgroup with baseline viral load >10⁵ copies/mL) will be included in the primary analysis. Viral load will be measured by a qRT-PCR test at Days 1 and 4. The analysis for the primary endpoint will focus on the log₁₀ viral RNA on Day 4. A repeated measures mixed model will be used to compare the two treatment groups. The mixed model will jointly model day 1 and day 4 viral load and will allow for the inclusion of all participants with at least one viral load assessment [Carpenter 2007]. The model will include fixed effects for treatment and age. Random effects will be included for subject and site. Linear contrasts will be used to compare the difference between groups for Day 4. This difference will be conditional on baseline viral load and is equivalent to an analysis adjusted for baseline [Carpenter 2007]. 95% CIs will be estimated for treatment differences at Day 4. A supportive analysis will be conducted using the ITT population, stratified by baseline viral load >10⁵ copies/mL vs. viral load ≤10⁵ copies/mL.

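### Section 12.4.6 tests heterogeneity of treatment effect with a subgroup-by-time interaction, which measures prognosis in the mixed model and cannot be estimated separately in the logistic model

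*Combined protocol and SAP*

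**What the plan says.** Section 12.4.6 plans HTE analyses by days from symptom onset to randomization, NEWS score and sex, for two outcomes: "HTE will be evaluated within a mixed model for the primary outcome and a logistic regression for the secondary progression outcome". One list of terms serves both models: "The models will include treatment, site, the subgroup variable, and the interaction of the subgroup variable with time". The decision rule follows: "The significance test of the interaction will be used to formally test HTE at the two-sided 0.05 significance level". The section also promises subgroup-specific results: "Differences in means or risk with 95% confidence intervals will be estimated for the treatment difference within each level of the subgroup variable".

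Two other sections show what time could mean in these models. For the primary outcome, Section 12.4.3 says "The mixed model will jointly model day 1 and day 4 viral load", so time there has two levels, one of them before dosing. For progression, Section 12.4.4.1 says "The proportion of those progressing to hospitalization or death within 28 days of randomization will be compared between treatment groups using logistic regression", which is one binary result per participant over a fixed window.

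Sections 12 and 12.4.1 leave fuller statistical detail to a SAP to be filed before database lock. No section of the document names a treatment-by-subgroup term.

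**The concern.** HTE is a difference in treatment effect between subgroup levels, so its test must involve treatment. The interaction in Section 12.4.6 does not.

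- **Mixed model.** Subgroup by time compares the change in viral load between subgroup levels with the arms pooled. Under 1:1 allocation it estimates the prognostic difference plus half of any difference in treatment effect, and it cannot tell the two apart.
- **Logistic model.** There is no time variable. If time is the constant 28-day window, subgroup by time is a multiple of the subgroup column.
- **Internal conflict.** Without a treatment-by-subgroup term, the fitted mean difference (or odds ratio) is the same at every level. The promised within-level differences then cannot show heterogeneity on those scales.

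Symptom duration and NEWS could plausibly predict clearance whatever the treatment. Applied as written, the rule could report that the drug works differently by symptom duration when those participants merely clear virus at a different rate. It could also miss a real difference that prognosis happens to offset.

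**Working it through.** **Plan's own figure.** Section 12.4.6 gives only the 0.05 level. The evaluable numbers come from Section 12.2, so that calculation was reproduced first. With Cohen's d = 0.60, two-sided alpha 0.20 and 90% power, n per arm = 2(1.2816 + 1.2816)²/0.60² = 36.5, rounded up to 37, or 74 in total, as stated. The power table also reproduces to within two points (0.801 to 0.982 computed, 0.79 to 0.98 stated).

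**Inputs from the document.** Enrolment is 142, with power shown "given 10% loss to follow-up and various proportions enrolled with baseline viral load" above the threshold. Evaluable numbers are 142 x 0.9 x 0.40 = 51, 142 x 0.9 x 0.50 = 64 and 142 x 0.9 x 1.00 = 128.

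**Assumptions not in the document.** Base case: 64 evaluable, two equal subgroups of 32, 1:1 treatment within each, SD 1 on both days, correlation 0.5. Prognostic shifts and HTE sizes are also assumed. Each scenario had 10,000 simulated trials. The subgroup-by-time test is the difference between subgroups in mean change, arms pooled. The comparison test is treatment by subgroup in an ANCOVA of Day 4 on baseline.

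**1. No HTE: effect 0.6 SD in both subgroups.** The variance of change is 2(1 − 0.5) = 1. Pooling the arms adds 0.6² x 0.25 = 0.09. The standard error is √(1.09 x 2/32) = 0.261. The expected z is shift/0.261.

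| Prognostic shift at Day 4 | Expected z | Subgroup x time rejects | Range* |
|---|---|---|---|
| 0 | 0 | 4% | 3–5% |
| 0.25 SD | 0.96 | 14% | 9–39% |
| 0.5 SD | 1.92 | 46% | 20–94% |
| 1 SD | 3.83 | 97% | 62% to over 99% |

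*51 to 128 evaluable, correlation 0 to 0.7, subgroup split 50:50 or 70:30.

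Treatment by subgroup rejects 4.5–5.7% throughout. Adding treatment by time to the model moves 46% to 50% and 97% to 98%. A separate simulation at a 0.6 SD shift gave 69% (N = 74) and 89% (N = 128). Fitting the mixed model itself at N = 128 (200 runs) gave 86.5%, against 5% for the three-way term.

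**2. Real HTE: effect 1.2 SD in one subgroup, 0 in the other.** The arm-averaged effect in the responding subgroup is 1.2/2 = 0.6 SD. The numerator is therefore 0.6 minus that subgroup's prognostic shift (positive = slower clearance). The variances are 1 + 1.2² x 0.25 = 1.36 and 1, so the standard error is √(2.36/32) = 0.272.

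| Shift in responders | Expected z | Subgroup x time | Treatment x subgroup |
|---|---|---|---|
| −0.6 SD | 4.42 | over 99% | about 77% |
| −0.3 SD | 3.31 | 92% | about 77% |
| 0 | 2.21 | 58% | about 77% |
| +0.3 SD | 1.10 | 17% | about 77% |
| +0.6 SD | 0 | 3% | about 77% |

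For the correct test, the residual variance is 1 − 0.5² = 0.75 and the standard error is √(0.75 x 4/16) = 0.433, so z = 1.2/0.433 = 2.77 at any shift. With a smaller HTE (0.6 SD versus 0), subgroup by time rejects 94%, 63%, 21%, 4% and 20% across the same shifts, against about 27% for the correct test (z = 0.6/0.433 = 1.39).

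**3. Reading time as treatment, without naming the day.** A two-way treatment-by-subgroup term averaged over Day 1 and Day 4 halves the contrast, because Day 1 is before dosing. The variance of the two-day mean is (1 + 0.5)/2 = 0.75, so the standard error is again 0.433 and z falls to 0.6/0.433 = 1.39. Power drops from 77% to 28% (1.2 SD) and from 27% to about 10% (0.6 SD).

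**4. Logistic model.** The columns intercept, treatment, subgroup and subgroup x 28 have rank 3 of 4. Replacing the last with treatment by subgroup gives rank 4 of 4. Without it, risk differences vary only through baseline risk: an assumed common odds ratio of 0.5 gives −2.4, −4.7 and −8.9 points at placebo risks of 5%, 10% and 20%.

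**The case against.** The strongest reply is that this is a slip with an obvious meaning. The section announces HTE as its target and promises treatment differences within levels, and an analyst would find at once that the logistic version cannot run. Term lists in this protocol are abbreviated: Section 12.4.3 lists only treatment and age as fixed effects, yet promises a Day 4 contrast. Detail is deferred to a SAP, which may put this right.

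Most of that is fair as to intent. It does not make the sentence correct. Section 12.4.6 states its own model and its own test, whereas the exploratory-endpoint and interim-analysis sections expressly refer to the SAP. Changing the one word is also not enough for the joint model, as step 3 of the working shows.

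A second objection is that the figures above include a time main effect, which Section 12.4.6 does not list. That is true, but omitting it makes matters worse. A 2-df test of the literal list at N = 64, with a non-prognostic subgroup and no HTE, rejects 52% if placebo does not decline and about 100% if it declines by 0.5 SD (assumed declines).

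Third, the prognostic shifts are assumed, and symptom days and NEWS have no stated categories. This stands: the percentages show how the test behaves, and do not predict the error in this trial. If a subgroup has no prognostic value, false rejection is not inflated.

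Finally, this is a subgroup analysis in a Phase II trial, and even the correct test has low power for modest HTE. That limits the importance of the point.

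**Conclusion.** The concern holds. As written, the formal HTE test is not a test of HTE for viral load, and for hospitalization or death it does not exist as a separate term. In the base case, false declarations of HTE rise from 4% to 97% as the prognostic shift goes from 0 to 1 SD. Detection of a real 1.2 SD difference runs from over 99% down to 3%, depending only on prognosis, against about 77% for the proper test. These sizes rest on the assumed correlation, subgroup split and shifts. The structural conclusion does not, except that the logistic aliasing takes time as the fixed 28-day window; a participant-specific time would make the term estimable but still not a measure of effect modification. The primary analysis, sample size and data collection are unaffected. It should be fixed, and confidence in the textual reading is high.

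**What to change.** In Section 12.4.6, replace the subgroup-by-time term with treatment by subgroup, specified for each outcome:

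- **Day 4 viral load:** treatment by subgroup at Day 4, adjusted for baseline viral load. If the joint Day 1/Day 4 model is kept, use treatment by subgroup by day with all lower-order terms, not a two-way term averaged over both days.
- **Hospitalization or death:** treatment by subgroup in the logistic model.

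Name that term as the HTE test at two-sided 0.05, and derive the within-level differences and intervals from the same model. The cost is one or two sentences in the protocol or SAP before database lock, with no added participants or data.
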